1.4 Pre-Clinical Experience

[figure not shown]
The innate immunomodulatory properties of MIS416 have been characterized extensively *in vitro* and *in vivo*. In vaccination models, MIS416 acts as a safe, potent cellular and humoral adjuvant without granuloma formulation or other adverse immune sequelae. When administered as a stand-alone prophylactic or therapeutic agent, MIS416 activates a broad range of innate host defense mechanisms which are able to prevent or ameliorate bacterial and viral infections in animal disease models. The ability of MIS416 to activate innate anti-neoplastic mechanisms has also been demonstrated in pre-clinical animal lung cancer studies.

A preliminary preclinical experimental autoimmune encephalomyelitis (EAE) animal model study identified that administration of MIS416 i.v at the time (d = 0) of immunization with MOG peptide in Freund's adjuvant s.c followed by pertussis toxin i.p on day 2 delays the onset and incidence of disease (Figure 1.5A) as well as reduces the disease score (Figure 1.5B). The maximum disease score is also significantly reduced in

Version 5

this treatment group (Figure 1.5C). Treatment with MIS416 on day -3 relative to MOG immunization preferentially enhances the recovery phase from disease (Figure 1.5D).

Figure 1.5

The ability of MIS416 therapy to modulate disease in mouse EAE model

When choosing animal models in which to evaluate test agents it is important to verify that the target receptor presumed to be present in the animal is present and that it recognizes the test agent ligand.

The ligands present on MIS416 are NOD-2 and TLR9. Both are evolutionarily conserved proteins present in all mammalian species¹⁵. These receptors recognize a unique pattern of molecules derived from pathogens or damaged cells, triggering robust but defined innate immune responses in all mammals.

The two species selected to evaluate acute and repeat dose toxicity arising from the administration of MIS416 were the out-bred mouse and rabbit. In common with all mammals, these two species have the NOD-2 and TLR9 receptor targets. In both species, these receptor targets also recognize the test agent ligands as evidenced by the extensive *in vitro* and *in vivo* mechanism of action studies in mice (Section 1.3) and the toxicity studies conducted in both these species. Specifically in both mice and rabbit

Version 5

repeat dose toxicity studies, recognition of the test agent's ligands was clearly demonstrated by biological responses consistent with the items mechanism of action. These included a dose responsive induction of histiocytic proliferation in target organs, extra medullary hematopoiesis in target organs, and in rabbits, liver oval cell (stem cell) proliferation.

1.4.1 Acute Dose Studies

GLP single ascending dose acute toxicity animal studies have been conducted to establish a maximum tolerable dose (MTD) in Swiss albino mice and NZ white rabbits.

In summary, in mice, (n=5M & 5F per group) two deaths occurred in males in each of the mid and high dose groups (30 and 45 mg/kg respectively) whereas there were no mortalities in the low and intermediate dose groups (10 and 15 mg/kg respectively). There was no treatment related gross pathology in males or females in any groups. Histopathology evaluation showed treatment related, dose dependent histiocytic proliferation in liver, increased extra medullar hematopoiesis in spleen, granulocytic infiltration in mandibular lymph nodes & leukocytic infiltration at site of injection in both males & females in all treated dose groups.

In view of the results observed, the MTD for MIS416 when administered as a single dose to Swiss albino mice by i.v. route was determined to be 15 mg/kg bodyweight under the test conditions and doses employed.

In rabbits (n=5M & 5F per group) dosed at 50, 200, 800, or 3200 µg/kg, there were no toxic signs or mortalities. There was no treatment related gross pathology in males or females in any groups. There was no treatment related microscopic changes in males or females in the high dose group (3200 µg/kg) compared to the control group. The maximum dose of 3200 µg/kg was selected based on earlier gross pathology findings in a non-GLP acute study in NZ white rabbits (n=2M & 2F per group) wherein bolus doses of 6, 18, 55, 166, and 500 µg/animal were tested. These doses approximated to 2.5, 7.5, 23, 70, and 200 µg/kg. In this study gross pathology was observed in spleen and liver of the high dose (200 µg/kg) group. A high dose of 3200 µg/kg was established for the GLP single ascending dose acute toxicity animal study on the basis that a 16-fold increase over the non-GLP study high does should have been sufficient to establish a MTD.

It did not, however the subsequent GLP four week repeated dose toxicity study did find significant pathology and one mortality (n=4M & 4F per group) in the high dose (5000 μ g/kg) group. This repeat dose study found a NOAEL of greater than 50 μ g/kg and less than 500 μ g/kg bodyweight under the test conditions and doses employed.

1.4.2 Repeat Dose Studies

GLP four week twice weekly and twenty six week once weekly repeated dose toxicity animal studies have been conducted to evaluate potential toxicity, look for corollaries with the protective effects of the test item previously identified *in vitro* and *in vivo*, and

Version 5

provide an estimate of No Observed Adverse Effect Level (NOAEL). The four week studies were conducted in Swiss albino mice and NZ white rabbits and the twenty six week study was conducted in NZ white rabbits.

1.4.3 4 Week Repeat Dose Studies

In mice (n=10M & 10F per group), there were were no treatment related adverse effects in the low dose group (1 mg/kg). In the mid dose group (3 mg/kg) treatment related gross pathology, an enlarged spleen, was found in one female and considered an adverse effect. Histopathology findings comprised a grade 1 lymphocytic infiltration in the urinary bladder in one female, a grade 3 histiocytic proliferation in liver in one female and grade 3 extramedullary hematopoiesis in liver in one female. These were considered adverse effects.

In the high dose group (10 mg/kg) treatment related gross pathology, enlarged spleens, were found in males and females. Histopathology findings comprised grade 1 and grade 2 lymphocytic infiltration in the urinary bladders of males and females, greater than grade 2 histiocytic proliferation in livers in males and female and greater than grade 2 extra medullary hematopoiesis in livers and spleens of males and females. These were considered adverse effects.

In view of the results NOAEL for MIS416 when administered twice weekly for 4 weeks to Swiss albino mice by i.v. route is greater than 1 mg/kg and less than 3 mg/kg bodyweight under the test conditions and doses employed.

In rabbits (n=4M & 4F per group), one death occurred in males in the high dose group (5000 μ g/kg) whereas there were no mortalities in the low and mid dose groups (50 and 500 μ g/kg respectively).

In the low dose group, desirable effects, consistent with the test items mode of action, were grade 1 histiocytic proliferation (activation of macrophages) in liver, grade 1 oval cell proliferation (activation of liver stem cell), and grade 1 bone marrow hypercellularity. Findings of grade 1 or grade 2 lymphoid hyperplasia in spleen in all males and females and grade 1 increased hemosiderous in spleen in a single female were considered treatment related but not adverse effects.

In mid and high dose groups there were findings of grade 1 and grade 2 desirable effects, consistent with the test items mode of action, comprising histiocytic proliferation in liver, lung, and spleen, oval cell proliferation, and bone marrow hypercellularity. Adverse findings, in particular in the high dose group, included treatment related adverse hematology and chemistry, organs weights, gross pathology and histopathology including erythrophagoctosis in liver and spleen, increased hemosiderosis (greater than grade 1) in spleen, lymphoid depletion in spleen, endothelial hyperplasia in lungs and eyes, and glomerular hypercellularity in kidneys.

Version 5

In view of the results NOAEL for MIS416 when administered twice weekly for 4 weeks to New Zealand white rabbits by i.v. route is greater than 50 μ g/kg and less than 500 μ g/kg bodyweight under the test conditions and doses employed.

1.4.4 26 Week Repeat Dose Study

In this GLP repeat dose toxicity study, respective groups of 6 animals per sex per group were administered MIS416 intravenously once weekly for 26 weeks with doses of 0 ug (control), 20 ug, 200 ug or 1000 ug /kg. Following the treatment period, 2 animals per group were held for a 4 week recovery period.

At the lowest dose of 20 μ g/kg there were no deaths. Principal effects included minimal leukocyte infiltration into the choroid of the eye, minimal portal inflammation in the liver, with no effects on liver enzymes, minimal mixed leukocyte infiltration in the lung in 2/8 animals, and lymphoid hyperplasia of the spleen in one of eight animals. Absolute and relative spleen weights were increased as well.

At the middle dose (200 μ g/kg) there was no mortality whereas at the high (1000 μ g/kg) dose three animals died or were sacrificed when observed to be in a moribund condition during the fourth and fifth month. Cause of death was attributed to cardiac myofibre degeneration and necrosis. This finding, or any cardiac findings, was not found in any other surviving animal at any dose. Additional effects seen at these doses included small but statistically significant reductions in red cell parameters, slight decrease in platelet counts, increased globulin values with a corresponding decrease in Albumin/Globulin (A/G) ratio, and decreased calcium (females only). Although occasional random increases in liver enzyme levels were seen in some animals, there was no clear nor consistent effect. Histopathological evaluation of tissues showed effects in the spleen (hyperplasia of the germinal center and hyperplasia of the red pulp), liver (portal inflammation, with necrosis and fibrosis at the high dose only), lung (mixed leukocyte infiltration), eye (mixed leukocyte infiltration of the choroid), and kidney (tubular degeneration and regeneration, glomerulopathy and heterophil infiltration in high dose animals only).

In conclusion, the intravenous administration of MIS416 to rabbits on a weekly basis resulted in toxicological effects at the high dose that included mortality (3/8 animals), generally mild clinical pathology findings and histopathological effects in the eye, heart, kidney, liver, lung and spleen. These findings had either resolved or showed advancing resolution at the end of the four-week recovery period. Some of these findings, except mortality, were noted at the middle dose. Effects noted at the lowest dose of 20 ug/kg/dose were substantially reduced in incidence, and were limited to minimal leukocyte infiltration in the eye, minimal portal inflammation in the liver (no effects on liver enzymes) and lymphoid hyperplasia in the spleen in 1/8 animals. Thus, the dose of 20 ug/kg/dose is considered the NOAEL for the administration of MIS416 weekly for 26 weeks.

Version 5

1.4.5 Animal Toxicology Studies Conclusions

Results from the above summarized studies to evaluate potential toxicity, look for corollaries with the protective effects of the test item previously identified in vitro and in vivo, and provide an estimate of MTD and NOAEL, support the selection and relevance of the animal species used, namely mice and rabbits. Certain histopathological and histology findings in both species were fully consistent with the test agent's mode of action indicating that the cellular targets and intracellular target ligands, were present in both species. Furthermore, the use of rabbits to evaluate agents with the potential to induce significant and unwanted inflammatory responses is well established.

In-human experience with MIS416 to date (see below) has established a desirable dose range from 1 μ g/kg to 10 μ g/kg based on inducing an initial pro-inflammatory response as evidenced by grade 1 to grade 2 flu like symptoms, in particular fever and chills. Comparing the in-human high dose (10 μ g/kg) with the mouse MTD of 15000 μ g/kg and the rabbit MTD of 3200 μ g/kg suggests significant margins of 1500 times and 320 times respectively.

A comparison of the same in-human dose (10 μ g/kg) with the mouse NOAEL of 1000 μ g/kg and the rabbit NOAEL of 50 μ g/kg further suggests margins of 100 times and 5 times respectively, when MIS416 is administered weekly for 4 weeks. For the administration of MIS416 weekly for 26 weeks, the comparison of the same in-human high dose (10 ug/kg) with the rabbit NOAEL of 20 ug/kg provides a safety margin of 2 times.

However, it should be noted that, in the 26-week rabbit study, the effects seen at the middle dose of 200 μ g/kg were primarily a result of extended pharmacological effects, were not explicitly adverse, and that the NOAEL could be considered to be 200 μ g/kg, or provide a margin of 20 time the human dose.

The nature of the target for MIS416 and the mechanism of action are such that following *in vivo* administration and accumulation of the drug by the reticuloendothelial system, a transient inflammatory response can be expected. Monitoring of patient serum for increased levels of pro-inflammatory cytokines demonstrates the transient nature of MIS416 immunostimulation (Figure 1-6). These findings are very important since they demonstrate that administration of a single bolus of MIS416 does not induce an uncontrolled "cytokine storm", with maximum levels of serum cytokines peaking within 24 hour post delivery, returning to baseline levels by 48 hours.

Analysis of MIS416 - treated patient blood for a sustained inflammatory response, or the occurrence of a "second wave" of inflammatory activity over a longer time period (14 days) demonstrates there is no prolonged inflammatory activity following MIS416

Version 5

dosing. This further demonstrates that MIS416 innate immunostimulation is well controlled *in vivo* (Figure 1-7).

[figure not shown]
Figure 1-6

MIS416 systemic administration induces a transient serum inflammatory cytokine response which peaks within 24 hours following administration. Blood serum was harvested and directly measured for multiple cytokine content using flow cytometry cytokine bead array methodology (Bender MedSystem)

Version 5

Figure 1-7

MIS416 therapy does not lead to the sustained induction or a "second wave "of inflammatory mediators. Peripheral blood serum was harvested from two individual healthy donors and from a patient who had received 1 mg of MIS416 7 days prior to blood sampling. Blood serum was assayed for TNF- α , IL-6 and IL-1 β levels using flow cytometry bead array methodology.

2. Rationale for Study Design

2.1 Developmental Context

Immunomodulators (or immune response modifiers) are currently under investigation and/or approved to treat a range of indications including inflammatory and autoimmune disorders - examples include Interferon beta for treatment of relapsingremitting Multiple Sclerosis (MS).

It is the intention to develop MIS416 further within the field of progressive MS, due to the promising results seen with compassionate use to date and the paucity of new agents appearing in this therapeutic area.

The study aims to determine the safety and tolerability of ascending multiple doses of MIS416, administered intravenously to patients with chronic progressive multiple sclerosis (MS). From this information, dose-limiting toxicity (DLT), maximum tolerated dose (MTD) and recommended Phase 2 dose (RP2D) will be defined.

Clinical experience with MIS416 to date has established a desirable dose range from between approximately 2 μ g/kg to 14 μ g/kg based on inducing an initial pro-inflammatory response as evidenced by grade 1 to grade 2 flu like symptoms, in particular fever and chills.

In the event that the study demonstrates that MIS416 is well tolerated and safe, the next step in the clinical development of the agent would be to conduct a randomized, blinded, controlled Phase 2B trial of the efficacy and safety of MIS416 in the treatment of patients with Secondary Progressive Multiple Sclerosis.

2.2 Rationale Dose-Escalation Phase

This dose-range finding study in a progressive MS patient group will enable the determination of a recommended Phase 2 dose for the controlled trial cited above and build on the early data available with regard to pharmacodynamics in this area. Due to the nature of the disease and the once-weekly administration of MIS416, a staged dose-escalation design has been incorporated into this first-in-man study with the goal of selecting a pharmacologically active but well-tolerated dose level (i.e., the MTD for 4 weeks of treatment) for further testing.

2.3 Rationale Dose-Confirmation Phase

Once such dose selection occurs, the intent of the dose-confirmation phase of this trial is to create a safety database sufficient to support longer-term exposure in the planned efficacy trial. This will be accomplished by (a) expanding the patient population exposed to this dose level and (b) prolonging exposure to 3 months. This will allow confirmation of the longer-term safety and tolerability of MIS416 before exposing a much larger population to a lengthier dosing regimen in the planned efficacy trial. Given the variable but generally progressive nature of multiple sclerosis, patients treated for 3 months will be observed closely not only for standard safety outcomes but also for changes in underlying disease status – both to rule out any adverse effect of MIS416 on disease progression and to document any anecdotal changes that may inform the selection of patients and/or endpoints for the initial efficacy trial.

2.4 Selection of Starting Dose (DE Phase)

A starting dose of 125 μ g (or approximately 2.5 μ g/kg based on a 'worst case' estimate of 50 kg patient weight) has been selected for the study. This starting dose is justified with reference to:

a). The simple margin between NOAEL's observed in the animal toxicology studies expressed as dose per weight. In the rabbit, the most sensitive species, this simple margin was 20-fold as recorded in the following table:

Version 5

| Safety Study | Reported NOAEL | Margin (based on bottom of the NOAEL range) |
|------------------------------------|----------------------------------|--|
| Mice: (Twice weekly, 4 weeks) | > 1000 µg/kg but < 3000 µg/kg | 400 x |
| Rabbits (Twice weekly, 4 weeks) | > 50 µg/kg but < 500 µg/kg | 20 x |

N.B.: In these safety studies, both mice and rabbits were dosed twice weekly whereas dosing in the proposed study in patients is once weekly.

b). The safety factor between the proposed starting dose, being a weekly exposure, and the conversion of equivalent (weekly) animal exposure to human equivalent doses (HED) based on body surface area and a 60 kg human. In rabbit, this safety factor, based on weekly exposure, is 15-fold as recorded in the following table. This exceeds the 'default safety factor' of 10 contained in FDA Guidance "Estimating the Maximum Safe Starting Dose in Initial Clinical Trials for Therapeutics in Adult Healthy Volunteers" issued July 2005. N.B. The conversion factors contained in the Guidance reference a 60 kg human, thus the proposed human starting dose has been expressed as 2.1 µg/kg to maintain equivalence.

| Table: Safety Factor of HED to Human Starting Dose (2.1 μ g/kg or 0.0021 mg/kg | ;) |
|--|----|
| based on weekly exposure | |

| Safety | NOAEL | Conversion | HED | Human | Safety Factor |
|---------|--------------|---------------|---------|------------|---------------|
| Study | (based on | Factor | (mg/kg) | Equivalent | (based on |
| | twice weekly | (animal dose | | Weekly | weekly |
| | dosing) | in mg/kg to | | Exposure | exposure of |
| | | HED in mg/kg) | | (mg/kg) | 0.0021 mg/wk) |
| Mice: | 1 mg/kg | 0.08 | 0.08 | 0.16 | 76 x |
| Rabbits | 0.05 mg/kg | 0.32 | 0.016 | 0.032 | 15 x |

c). The limited 'compassionate use' experience to date in humans with progressive MS. The following table records for each of these patients the starting dose, maximum dose, and total number of doses received to date.

Version 5

4.1 Overview of Study Design

This is a single center, open-label, non-randomized, dose-escalation study, to be conducted in two phases: a dose-escalation (DE) phase, to evaluate the safety, tolerability, MTD, and PD of MIS416 administered IV once weekly for 4 doses; and a dose-confirmation (DC) phase, which will be a cohort expansion at or below the MTD (i.e., the RP2D) of MIS416, dosed once weekly for up to 12 doses.

Subjects will be treated with a weekly IV dose of MIS416 in 28-day cycles: 1 cycle in the DE phase, and up to 3 cycles in the DC phase. The initial dose of MIS416 will be 125 μ g/week. Subjects will be evaluated and dosed weekly each cycle in each phase. Subjects will return for a follow-up visit 15 days after completion of the last dose of study drug.

4.2 Number of Subjects Planned

The total number of subjects to be enrolled in the study is dependent upon the observed safety profile, which will determine the number of subjects per dose level, as well as the number of dose escalations required to achieve the MTD. It is anticipated that approximately 27-33 subjects will be enrolled in this study, with approximately 12-18 subjects in the dose-escalation phase and up to a further 15 subjects in the dose-confirmation phase. The study will be conducted at a single site.

4.3 Dose Escalation Phase (1 cycle only)

In the DE phase, the dose of MIS416 will be escalated in successive cohorts of 3 subjects per dose level. The first subject of each cohort will be dosed at least 48 hours prior to the rest of the cohort. If none of the 3 subjects at a dose level experience a DLT (see Section 4.4), then 3 new subjects may be entered at the next higher dose level. If 1 of 3 subjects experiences a DLT, 3 more subjects will be started at the same dose level (total of 6 subjects in cohort). If no additional subjects experience DLT at that dose, the next

higher dose level cohort will be initiated. If 2 or more subjects experience DLT, no further subjects will be started at that dose, MTD will be declared, and dose-escalation will cease (subject to confirmation by the Safety Review Team).

In the event that a single subject in a cohort experiences a DLT, the dose escalation increments will be reduced by at least 50% in the subsequent cohort. Any subject experiencing a DLT during the DE phase will be withdrawn from the trial.

The MTD is defined as the highest dose level at which < 2 of 6 subjects develop DLT. New dose levels may begin accrual only if all subjects at the current dose level have been observed for a minimum of 7 days from the 4th dose of the Cycle 1. The RP2D will be the MTD; if no MTD is reached, RP2D will be determined based upon evaluation of all clinical and PD data.

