Dose-Confirmation Phase (up to 3 cycles of treatment): The DC phase will not begin until the Sponsor has submitted to the Ethics Committee and regulatory authority the requisite sub-chronic nonclinical safety data, and received approval to proceed to 3 cycles of dosing. In the DC phase, up to 15 subjects will be recruited at the RP2D. The Safety Team will have the responsibility of reviewing safety data from the DC phase of the trial and making recommendations regarding dose modifications. If a DC phase subject withdraws from dosing within the first 2 cycles for reasons unrelated to drug toxicity, the subject may be replaced at the discretion of the Safety Review Team.

Dose-Limiting Toxicity (DE phase only): A DLT is a clinically significant adverse event (AE) or laboratory abnormality assessed by a Co-Principal Investigator as at least possibly related to the study drug and unrelated to disease progression, concurrent illness, or concomitant medications occurring during the DE phase of the trial. Toxicity will be graded and recorded according to Toxicity Grading Scale for Healthy Adult and Adolescent Volunteers Enrolled in Preventive Vaccine Clinical Trials, modified to include a Systemic line item for Rigors/Chills (Appendix 3).

A DLT is defined as:

- Grade 3 or 4 adverse event, except for fatigue and fever and/or rigors/chills.
- Grade 4, or an increase above baseline by 2 or more grades, fatigue.
- Grade 4 fever and/or rigors/chills.

Intra-Subject Dose Reduction (DC phase only): An individual subject's dose may be reduced to the next lower cohort dose level (ie, as determined from the DE phase), at the Co-Principal Investigators' discretion and with the approval of the Sponsor, following a DLT or other clinically significant toxicity. The dose may not be reduced below 125 μ g/week.

Name of Sponsor/Company: Innate Therapeutics Limited

Name of Product: MIS416

Duration of Treatment: Each treatment cycle will be 28 days of weekly dosing (ie, 4 doses). This trial will entail 1 cycle of treatment in the DE phase and up to 3 cycles of treatment in the DC phase.

Criteria for Evaluation:

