4.4 Dose Limiting Toxicity (DE phase only)

A DLT is a clinically significant adverse event (AE) or laboratory abnormality assessed by the Co-Principal Investigators as at least possibly related to the study drug and unrelated to disease progression, concurrent illness, or concomitant medications, occurring within Cycle 1. Toxicity will be graded and recorded according to the Toxicity Grading Scale for Healthy Adult and Adolescent Volunteers Enrolled in Preventative Vaccine Clinical Trials (presented in the companion Operations Manual), modified to include a systemic line item for rigors/chills and an amendment to the classification of pyrexia (Appendix 3). A DLT is defined as:

- Grade 3 or 4 adverse event, except for fatigue and fever and/or rigors/chills
- Grade 4, or an increase above baseline of 2 or more grades, fatigue
- Grade 4 fever and/or rigors/chills.

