4.6 Intra-Subject Dose Reduction (DC phase only)

An individual subject's dose may be reduced to the next lower cohort dose level (ie, as determined from the DE phase), at the Co-Principal Investigator's discretion and with

the approval of the Sponsor, following a grade 4 or other clinically significant toxicity. The dose may not be reduced below 125 μ g/week.

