11.2 Maximum Tolerated Dose

The MTD will be declared by the Safety Review Team, when at least 2 out of six subjects in a cohort experience a DLT. The MTD will be determined as the next lower dose in which <2 subjects experienced a DLT.

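### The MTD is defined on six subjects, but the escalation rules allow it, and so the RP2D, to be declared on three; the related MTD, RP2D and dose-reduction wording also conflicts.

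*Protocol*

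**What the plan says.** **MTD definition.** Section 4.3, repeated in the synopsis, says: "The MTD is defined as the highest dose level at which < 2 of 6 subjects develop DLT".

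**Clearing a level.** Section 4.3 also says that "the dose of MIS416 will be escalated in successive cohorts of 3 subjects per dose level", and: "If none of the 3 subjects at a dose level experience a DLT (see Section 4.4), then 3 new subjects may be entered". A cohort grows to six only after exactly 1 DLT in the first 3. Two or more DLTs at a level end escalation, whatever the cohort size.

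**Naming the MTD.** Section 11.2 triggers the declaration at two or more DLTs out of six, and then: "The MTD will be determined as the next lower dose in which <2 subjects experienced a DLT". It gives no denominator for the lower dose.

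**RP2D.** Section 4.3 sets the RP2D equal to the MTD, or bases it on all clinical and PD data if no MTD is reached. Section 4.1 and the synopsis design paragraph place the expansion at or below the MTD and call that dose the RP2D.

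**DC dose reduction.** The synopsis allows reduction "following a DLT or other clinically significant toxicity", although both the synopsis and Section 4.4 confine DLTs to the dose-escalation (DE) phase. Section 4.6 allows it "following a grade 4 or other clinically significant toxicity".

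**The concern.** The MTD and RP2D are primary outputs of the trial, and Section 2.2 intends the dose for a later controlled study. A reader of Section 4.3 will take the MTD to be a dose at which six subjects were observed with at most one DLT. The operating rules do not guarantee that. Suppose a level shows 0/3 and the next shows two or more DLTs. Section 11.2 then points back to a level with three subjects, while the Section 4.3 definition calls for six. Nothing in the protocol says which prevails or whether three more subjects are to be entered. Two teams following the same text could declare different MTDs from the same data. The report could also attach the six-subject property to a dose that never had six DLT-evaluable subjects.

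**Working it through.** **Inputs.** The escalation rule is from Section 4.3, the table of escalation probabilities from Section 14.1, and the DC size of up to 15 from Section 4.5. The protocol assumes no DLT rates, so a range is shown.

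**Step 1: reproduce the plan's own table.** With true DLT rate p at a level,

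P(escalate) = (1−p)³ + 3p(1−p)² × (1−p)³.

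At p = 0.3: 0.343 + 0.441 × 0.343 = 0.343 + 0.151 = 0.494; the table gives 49%. All nine rates reproduce: 90.6, 70.9, 49.4, 30.9, 17.2, 8.2, 3.2, 0.9 and 0.1%. The table is correct for the written rule and confirms that 0/3 is meant to clear a level.

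**Step 2: how often a cleared level has only three subjects.**

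P(0/3 | cleared) = (1−p)³ / P(escalate) = 1 / [1 + 3p(1−p)²].

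| True DLT rate | Cleared, as written | Share cleared on 0/3 | ≤1 DLT if six always observed |
|---|---|---|---|
| 10% | 90.6% | 80.5% | 88.6% |
| 20% | 70.9% | 72.3% | 65.5% |
| 30% | 49.4% | 69.4% | 42.0% |
| 40% | 30.9% | 69.8% | 23.3% |

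The last column is the chance of meeting the definition literally. The written rule passes a level more often by 2.0, 5.3, 7.4 and 7.6 percentage points respectively.

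**Step 3: across four levels.** Exact enumeration under assumed DLT curves (5-10-20-35%, 10-20-30-50%, 2-5-10-20%, flat 10%, flat 20%) gives 72% to 80% of selected doses resting on three subjects. This counts the top level when it is cleared. The curves are assumptions.

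**Step 4: what 0/3 shows.** The exact two-sided 95% upper limit for 0/n is 1 − 0.025^(1/n). For n = 3 it is 70.8%; for n = 6 it is 45.9%. For 1/6 the exact interval is 0.4% to 64.1%. A dose with a true DLT rate of 30% shows 0/3 with probability 0.7³ = 34%; at 40% the probability is 0.6³ = 22%.

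**Step 5: the two dose-reduction triggers.** Under Section 4.4 a DLT includes Grade 3 events other than fatigue, fever and rigors/chills, and fatigue two or more grades above baseline. The synopsis trigger would cover these if DLTs were scored in DC. Section 4.6 names only Grade 4. Both texts add other clinically significant toxicity, which narrows the practical gap but does not remove it.

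**Step 6: what DC Cycle 1 could add.** With three DE subjects and the full 15 DC subjects, n = 18. The exact 95% upper limit is 18.5% for 0/18, 27.3% for 1/18 and 47.6% for 4/18. No event in 15 has probability 0.9¹⁵ = 20.6% at a true rate of 10%, 3.5% at 20% and 0.5% at 30%, so the first figure is a favourable case.

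**The case against.** Several points on the other side stand.

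- **The chosen dose is not short of safety data.** A reader might infer that it rests on almost none. Section 2.3 makes wider and longer exposure the purpose of DC. DC adverse events are graded on the same scale (Sections 7.1 and 12.2.2), overseen by the Safety Review Team (Sections 4.5 and 4.8), tabulated by grade and relationship (Section 14.5.3.2) and included in toxicity rates for all treated subjects (Section 14.2.2).
- **Confining formal DLTs to DE is coherent.** A reader might call it an error, but DLTs drive escalation, and escalation happens only in DE.
- **Escalation after 0/3 is not automatic.** New subjects may be entered only after at least 7 days' observation from the fourth dose, and the Safety Review Team decides.
- **Section 4.3 need not name the toxic dose.** Its stopping sentence might be read as declaring the MTD there, but its own definition and Section 11.2 both exclude that.
- **The 2-of-3 gap in Section 11.2 has little effect.** Two DLTs in three already ensure at least two in six, so the outcome would be the same.

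It can also be argued that a three-subject level is simply not yet an MTD under Section 4.3, so that the RP2D would rest on all clinical and PD data. That reading is possible, but it sets aside Section 11.2, which names such a level as the MTD. Having two defensible readings is the defect, and Safety Review Team judgement does not cure it while the definitions conflict.

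**Conclusion.** The concern holds as an internal inconsistency in the rule for a primary output. As written, a level with three subjects can be named MTD and RP2D without meeting the six-subject definition. At true DLT rates of 10% to 40%, 69% to 80% of cleared levels are in that position, and 0/3 is compatible with a DLT rate of up to 71%. These figures assume independent subjects and the Section 4.3 rule applied literally. The two RP2D statements and the two dose-reduction triggers also conflict.

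The documents do not support the larger claims that the escalation table is wrong, that the dose goes forward without safety evidence, or that DLTs must be scored in DC. Nor would 18 to 21 subjects at the RP2D be assured. Fifteen is a ceiling for DC, the Safety Review Team sets its size and dose, and DC doses may be reduced.

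**What to change.** **Required.** Reconcile the synopsis and Sections 4.1, 4.3 and 11.2 into one MTD/RP2D rule that states how many subjects must have been observed at the dose declared as MTD. Alternatively, restate the six-subject property so that it describes what the rules deliver. Use one stopping trigger throughout and say whether the RP2D equals the MTD or may lie below it. Reconcile the dose-reduction trigger in the synopsis with Section 4.6. The choice of rule belongs to the sponsor. The cost is amendment wording; if the six-subject property is kept, it also means three further subjects at any 0/3 level that has to be completed.

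**Optional and descriptive.** Tabulate events meeting the Section 4.4 criteria in Cycle 1 of DC subjects, shown for DE, DC and pooled with exact 95% intervals. The data are already collected under Table 3, so the cost is one table. DC differs from DE: SPMS only, an echocardiogram exclusion, antipyretic pre-medication and permitted dose reduction. The pooled figure should therefore be secondary to the results by phase, and its precision will depend on the events seen.
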